6.5.1.3. Derivation of Symptomatic SARS-CoV-2 Infection (COVID-19)

The incidence of symptomatic SARS-CoV-2 infection starting 14 days after randomization is an exploratory endpoint in Part 1 and a secondary endpoint in Part 2. Surveillance for COVID-19 symptoms will be conducted via safety calls throughout the duration of the study and blood draw from scheduled visits. Participants reporting certain COVID-19 symptoms will be arranged an unscheduled visit to collect an NP swab.

Symptomatic SARS-CoV-2 infection will be defined in the following two ways:

1. Protocol-defined COVID-19 case definition (primary case definition): Cases to be defined as meeting clinical criteria based on both symptoms of COVID-19 and positive RT-PCR test results as outlined in [Table 6](#).
2. CDC Case Definition of COVID-19 (secondary case definition): Cases will be identified as a positive post-baseline RT-PCR test result that is prompted by symptom(s), together with eligible symptoms, i.e., a positive PCR result of the eligible symptoms summarized below in [Table 7](#).

Table 6 Derivation of Symptomatic COVID-19 (primary case definition)

Post-baseline PCR results	Positive, AND
Systemic Symptoms	at least TWO of the following systemic symptoms : Fever ($\geq 38^{\circ}\text{C}/\geq 100.4^{\circ}\text{F}$), chills, muscle and/or body aches (not related to exercise), headache, sore throat, new loss of taste/smell; OR
Respiratory Symptoms	at least ONE of the following respiratory signs/symptoms: cough, shortness of breath and/or difficulty breathing, OR clinical or radiographical evidence of pneumonia.

Table 7 Derivation of Symptomatic COVID-19 (secondary case definition)

	COVID-19 (CDC criteria)
Post-baseline PCR results	Positive, AND
Systemic Symptoms	at least ONE of the following systemic symptoms: Fever ($\text{temperature} \geq 38^{\circ}\text{C}/\geq 100.4^{\circ}\text{F}$) or chills, fatigue, muscle and/or body aches (unrelated to exercise), headache, congestion or runny nose, new loss of taste or smell, sore throat, or vomiting or diarrhea; OR
Respiratory symptoms	at least ONE of the following respiratory signs/symptoms: cough, shortness of breath or difficulty breathing.

The date of documented COVID-19 (case) will be the later date of the eligible symptom(s) and date of positive PCR test and the two dates should be within 14 of each other. Specifically, for the primary definition, the date of the documented COVID-19 will be later date of:

- Date of the positive RT-PCR test,
- Date of eligible symptom(s), defined as earliest of
 - Systemic symptoms: earliest date of the 2nd eligible systemic symptom is reported
 - Respiratory symptom: earliest date of an eligible respiratory symptom is reported

For the secondary definition of a COVID-19 infection, the date of documented COVID-19 will be the later date of:

- Date of positive RT-PCR test,
- Date of eligible symptom(s), defined as earliest of
 - Respiratory symptom: earliest date of an eligible respiratory symptom is reported
 - Systemic symptoms: earliest date of the eligible systemic symptom is reported

The time to the first occurrence of COVID-19 will be calculated as:

Date of documented Case Definition of COVID-19 – Date of randomization + 1.

Cases will be counted starting 14 days post randomization, i.e., date of documented COVID-19 – Date of randomization \geq 14.

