
To assess for symptomatic and asymptomatic SARS-CoV-2 infection after vaccination with mRNA-1273.214 booster or mRNA-1273 booster
	
Reverse transcriptase polymerase-chain reaction (RT-PCR)-confirmed symptomatic or asymptomatic SARS-CoV-2 infection will be defined in participants based on the following criteria:
 
 • Protocol-defined COVID-19 case definition 
 ○ The participant must have experienced at least TWO of the following systemic symptoms: Fever ($\geq 38^{\circ}\text{C}$), chills, myalgia, headache, sore throat, new olfactory and taste disorder(s), OR ○ The participant must have experienced at least ONE of the following respiratory signs/symptoms: cough, shortness of breath or difficulty breathing, OR clinical or radiographical evidence of pneumonia; AND ○ The participant must have at least one nasopharyngeal (NP) swab, nasal swab, or saliva sample (or respiratory sample, if hospitalized) positive for SARS-CoV-2 by RT-PCR. • Center for Disease Control (CDC) defined COVID-19 definition based on the CDC criteria: the presence of one of the CDC listed symptoms (https://www.cdc.gov/coronavirus/2019-ncov/symptoms-testing/symptoms.html) and a positive RT-PCR test on a respiratory sample • Asymptomatic SARS-CoV-2 infection is defined as a positive RT-PCR test on a respiratory sample in the absence of symptoms or a positive serologic test for antinucleocapsid antibody after a negative test at time of enrollment
Exploratory Objectives	

To evaluate cellular immunogenicity in a subset of participants
	
 • Frequency, magnitude, and phenotype of virus-specific T-cell and B-cell responses measured by flow cytometry or other methods, and to perform targeted repertoire analysis of T-cells and B-cells after vaccination

To evaluate the genetic and/or phenotypic relationships of isolated SARS-CoV-2 strains to the vaccine sequence
	
 • Characterize the SARS-CoV-2 spike genetic sequence of viral isolates and compare with the vaccine sequence • Characterize the immune responses to vaccine breakthrough isolates

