8.9.2. Assessments for SARS-CoV-2 Infection

Study participants will have NP swab samples collected for SARS-CoV-2 testing as specified in the SoE (Table 1 and Table 2).

For the duration of the study, participants will be directed as soon as possible and within 24 hours to obtain an approved/authorized PCR test for SARS-CoV-2 locally outside of the study according to prior National Health Service (NHS) guidance if they experience symptoms of COVID-19 as previously defined by the NHS:

- High temperature (feel hot to touch on the chest or back)
- A new, continuous cough (coughing a lot for more than an hour, or 3 or more coughing episodes in 24 hours, or worse than usual cough)
- A loss or change to sense of smell or taste

If a PCR test is unavailable locally, participants will be requested to come in for a study visit or take an approved/authorized lateral flow/rapid antigen test for SARS-CoV-2.

Participants will be directed as soon as possible and within 24 hours to take an approved/authorized lateral flow/rapid antigen test for SARS-CoV-2 if they experience any of the following (but do not meet the symptoms of COVID-19 as previously defined by the NHS and described above):

- Signs or symptoms of SARS-CoV-2 infection as defined by the CDC (<https://www.cdc.gov/coronavirus/2019-ncov/symptoms-testing/symptoms.html>) with modifications:
 - Chills
 - Cough (not meeting COVID-19 symptoms defined by the NHS)
 - Shortness of breath or difficulty breathing
 - Fatigue
 - Muscle or body aches
 - Headache
 - Sore throat
 - Congestion or runny nose
 - Nausea or vomiting
 - Diarrhea

Lateral flow/rapid antigen test for SARS-CoV-2 may be repeated every 24-48 hours if participants continue to have symptoms above.

Participants will be directed to take an approved/authorized lateral flow/rapid antigen test for SARS-CoV-2 within 4 to 6 days after last exposure* (see definition of last exposure below) if a participant experiences the following:

- Known close contact with someone who has known COVID-19 or SARS-CoV-2 infection. Examples include:
 - Being within 2 meters (without PPE) for a total of 15 minutes or more
 - Providing care at home
 - Having direct physical contact (hugged or kissed them)
 - Sharing eating or drinking utensils
 - Being sneezed or coughed upon or getting respiratory droplets on the participant

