**Last exposure is defined as the last day a participant was in close contact with a symptomatic person in the household (if the participant was then isolated from that person) or the last day of the quarantine of the person the participant was exposed to, if that person was asymptomatic and/or the participant was unable to isolate from that person.*

A study illness visit (study site visit) will be arranged as soon as possible and within 72 hours for participants who test positive or equivocal for SARS-CoV-2 using an authorized/approved lateral flow/rapid antigen or local PCR testing. If a test for SARS-CoV-2 is unavailable or if there is uncertainty on the test result, a study site visit may be arranged as soon as possible and within 72 hours.

At this visit, an NP swab will be collected to evaluate for the presence of SARS-CoV-2 infection.

Active surveillance for COVID-19 will be conducted throughout the study as described in the SoE ([Table 1](#) and [Table 2](#)).

All cases that have RT-PCR-confirmed COVID-19 as defined by the NHS or the CDC should be captured as MAAEs (unless the definition of an SAE is met) along with relevant concomitant medications, hospitalizations, outpatient medical care, and details about severity, seriousness, and outcome. Clinical information including but not limited to the following should be collected, if applicable: clinical assessment or imaging (including percentage of lung infiltrates), oxygen saturation (SpO₂), respiratory rate, and hospital course including (but not limited to) PaO₂/FiO₂ ratio, respiratory failure, oxygen support, shock, organ dysfunction, and life-sustaining treatment.

In addition to SARS-CoV-2 assessment and testing outlined in this protocol, also follow local testing guidelines.

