 - Secondary case definition based on the Center for Disease Control and Prevention (CDC) criteria: the presence of one of the CDC listed symptoms (<https://www.cdc.gov/coronavirus/2019-ncov/symptoms-testing/symptoms.html>) and a positive RT-PCR test on a respiratory sample.
 - Asymptomatic SARS-CoV-2 infection is defined as a positive RT-PCR test on a respiratory sample in the absence of symptoms or a positive serologic test for antinucleocapsid antibody after a negative test at time of enrollment.

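### SAP 6.5.1.3 adds a symptom-prompted PCR condition to the CDC COVID-19 case that the protocol, SAP 3.2.1 and Table 7 do not have; separately, Table 7 omits nausea

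*SAP*

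**What the plan says.** Symptomatic infection is exploratory in Part 1 and a secondary endpoint in Part 2. It has a primary (protocol-defined) and a secondary (CDC) case definition.

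- Protocol Section 3, Table 4 gives the CDC "defined COVID-19 definition based on the CDC criteria: the presence of one of the CDC listed symptoms", together with a positive RT-PCR on a respiratory sample. SAP 3.2.1 repeats this: "the presence of one of the CDC listed symptoms" plus a positive RT-PCR. Neither mentions the reason for the swab.
- SAP 6.5.1.3, item 2, turns this into a derivation: "Cases will be identified as a positive post-baseline RT-PCR test result that is prompted by symptom(s), together with eligible symptoms". It then refers to Table 7.
- Table 7 asks only that the post-baseline PCR be positive. Its systemic symptoms end with "new loss of taste or smell, sore throat, or vomiting or diarrhea". Nausea is not there.
- Protocol 8.9.2 includes "Nausea or vomiting" in its list of symptoms attributed to the CDC, with modifications.
- The dating rule in SAP 6.5.1.3 takes the later of the symptom date and the PCR date. The two must lie within 14 of each other, with no unit given.
- SAP 6.5.1.2 calls an infection asymptomatic if there are no COVID-19 symptoms in the 14 days either side of the positive test. It does not say which symptom list applies.
- SAP Section 1 lets the SAP override the protocol where methods differ. SAP Section 7, on changes from the protocol, says that none apply.

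**The concern.** A PCR that no symptom prompted is routine in this trial: the Schedule of Events takes a nasopharyngeal swab from every participant at four post-baseline visits. A condition on why the PCR was done therefore changes who is a case. It enters only in the derivation text, without being declared, in a document that overrides the protocol. Protocol Section 9 expects a change to secondary objectives or related methods to come by amendment, and changes to other secondary analyses to be listed in the SAP or the study report.

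Two programmers could build different CDC case flags from this one section. One would follow item 2 and need a record of what prompted each swab. The other would follow Table 7 and the dating rule and need only a positive result and a symptom date. The CDC counts, incidence rates and any efficacy estimate based on them would then differ.

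The missing nausea item is a second, independent departure from the symptom list that the protocol itself prints.

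**Working it through.** The plan gives no expected number of COVID-19 cases and no power for efficacy, so there is no planned figure to reproduce. The check is to send example participants through each rule.

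**Inputs**

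- Scheduled post-baseline swabs: Days 29, 85, 179 and 359 (Schedule of Events, both parts).
- Primary case (SAP Table 6): positive PCR plus two listed systemic symptoms or one respiratory sign. There is no prompting condition, and fatigue and nausea are not listed.
- CDC case, literal reading: item 2 of SAP 6.5.1.3.
- CDC case, alternative reading: Table 7 plus the later-of-two-dates rule.
- Asymptomatic infection: SAP 6.5.1.2.
- Overall infection: SAP 6.5.1.1, which accepts any positive post-baseline PCR.

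Each participant below is baseline negative and at least 14 days past randomization. The only positive PCR is from a scheduled swab, and the symptom lies within 14 days of it.

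| Symptom | Primary (Table 6) | CDC, item 2 read literally | CDC, Table 7 and dating rule | Asymptomatic | Overall infection |
|---|---|---|---|---|---|
| Cough | Yes | No | Yes | No | Yes |
| Fatigue alone | No | No | Yes | No | Yes |
| Nausea alone | No | No | No | Depends on the list used | Yes |

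**Row 1.** The participant stays a symptomatic case under the primary definition and is lost only from the CDC count.

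**Row 2.** The participant meets neither symptomatic definition. Fatigue is on both the Table 7 and the protocol 8.9.2 lists, so under either one the infection is not asymptomatic. It survives only as an overall infection. One Table 6 systemic symptom alone, such as headache, gives the same result.

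**Row 3.** The result does not depend on prompting. A swab taken because of nausea would also fail, since nausea is not a Table 7 symptom. If 6.5.1.2 borrows the Table 7 list, this person is counted as asymptomatic. If it uses the protocol 8.9.2 list, the person is in neither class.

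**Does the rest of SAP 6.5.1.3 support the literal reading?** No. Table 7's PCR row has no such condition. Dating a case by the later of symptom and PCR lets the symptom follow the swab, which does not fit a rule that the symptom must have triggered it.

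**Size.** Let N be the number of CDC cases under Table 7 and the dating rule, and s the share whose only positive PCR was unprompted. The literal count is N × (1 − s), so the count falls by the fraction s. The documents give neither N nor s.

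**The case against.** The strongest reply is that this is a drafting slip with little behind it. Table 7 and the dating rule already point to the unrestricted reading. Protocol 8.9.2 sends symptomatic participants for testing within 24 hours and arranges an illness visit and swab for "participants who test positive or equivocal for SARS-CoV-2 using an authorized/approved lateral flow/rapid antigen or local PCR testing". The eDiary also asks about COVID-19 every two weeks from Day 43. A loss therefore needs something further: a missed test, a negative lateral flow result, or symptoms that begin around or after a scheduled swab. No hypothesis, alpha or power attaches to efficacy.

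All of that is correct, and it limits the consequence. It does not remove the conflict. Item 2 is the operative sentence, the SAP prevails over the protocol, and the lateral flow sensitivity analyses in SAP 6.5.3 do not say that the condition is lifted.

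On nausea, one can reply that the case definition refers to a CDC web page and that the 8.9.2 list is a testing trigger with modifications. The documents alone cannot show what that page contained. They do show that the protocol's printed list and Table 7 disagree.

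A reader might also infer that every exposure-triggered positive with symptoms is lost. That is not supported. Exposure leads first to a lateral flow test, and the swab follows a positive or equivocal result. Whether such a swab in a symptomatic person counts as prompted by symptoms is simply undefined.

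**Conclusion.** The concern holds as a contradiction within the SAP and between the SAP and the protocol, with an undeclared narrowing if item 2 is followed literally. The nausea omission is a separate defect that applies to every swab.

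The effect is limited to counts and incidence under the secondary (CDC) case definition and to the symptomatic/asymptomatic split. Primary-definition cases and overall infections do not change. The rule is identical in both arms, and no primary or key secondary conclusion depends on it.

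Stronger readings that the documents do not support:

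- *Symptomatic infections drop out of the Part 2 secondary endpoint.* Those meeting Table 6 remain in it under the primary definition.
- *The loss is 8% to 16%.* Assuming 7 to 14 days of PCR positivity (not in the documents), 4 × 7 / 358 = 7.8% and 4 × 14 / 358 = 15.6%. That is the share of all infections that scheduled swabs could detect. It includes asymptomatic infections and people also swabbed for symptoms, so it is not s.
- *The clause alone breaks the nesting of definitions and the adding-up of classes.* Both already fail. Table 6 accepts clinical or radiographic pneumonia, which Table 7 does not list. A symptomatic seroconverter without a positive PCR is an infection but neither asymptomatic nor COVID-19.

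The fatigue example assumes that 6.5.1.2 uses the Table 7 or the protocol 8.9.2 list.

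**What to change.** 1. In SAP 6.5.1.3, item 2, strike the condition that the PCR be symptom-prompted. A CDC case is then any positive post-baseline RT-PCR, from a scheduled or unscheduled visit, with at least one Table 7 symptom inside the stated window.
2. State the unit of that 14 as days, as SAP 6.5.1.2 already does for its own window.
3. Add nausea to Table 7, to agree with protocol 8.9.2.
4. In SAP 6.5.1.2, say that the absence of COVID-19 symptoms is judged on the same list.

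If the sponsor does want the restriction, it should be defined (including for swabs that follow a positive lateral flow test), declared in SAP Section 7 and handled as protocol Section 9 requires.

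The cost is SAP wording and one derivation flag. No new data are needed, provided nausea is among the symptoms recorded; protocol 8.9.2 suggests that it is, but the case report form is not shown. The CDC count becomes slightly higher. Any nausea-only infection that would have been classed as asymptomatic moves to symptomatic.

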6.5.2. Analysis Method

The number and percentage of participants who had each type of event (i.e., an asymptomatic or a symptomatic SARS-CoV-2 infection) will be summarized in the PPSE.

As per Phase B, participants are allowed to receive an additional booster outside of the study. Participants who received this additional booster may be censored in the efficacy analyses at the time of booster, as outlined below.

The incidence rate of each type of event will be calculated as the number of cases divided by the total person-time. Person-time is defined as the total time from randomization date to the date of event, last date of study participation, censoring time, date of additional booster outside of the study or efficacy data cutoff date, whichever is earlier.

The 95% CI of the incidence rate will be calculated using the exact method (Poisson distribution) and adjusted by person-time.

Vaccine efficacy and the respective 95% CI will also be estimated.

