6.5.1. Endpoint Definition/Derivation

6.5.1.1. Derivation of SARS-CoV-2 Infection

SARS-CoV-2 infection will be defined in participants with negative SARS-CoV-2 status pre-booster by either:

- bAb levels against SARS-CoV-2 nucleocapsid protein negative (as measured by *Roche Elecsys*) at Day 1 that becomes positive (as measured by *Roche Elecsys*) post-baseline, OR
- Positive RT-PCR post-baseline.

The date of documented infection will be the earlier of:

- Date of positive post-baseline RT-PCR result, or
- Date of positive serology test result based on bAb specific to SARS-CoV-2 nucleocapsid

The time to the first SARS-CoV-2 infection will be calculated as:

Time to the 1st SARS-CoV-2 infection = Date of the 1st documented infection – Date of randomization + 1.

Cases will be counted starting 14 days after the randomization, i.e., date of documented infection – date of randomization \geq 14.

The incidence of SARS-CoV-2 infection counted starting 14 days after randomization will be summarized by treatment group.

Supportive analyses will summarize incidence of SARS-CoV-2 infection in which a case is counted after randomization, i.e., date of documented infection – date of randomization \geq 0.

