Window Allowance (Days)	-28		+3	+3	+3	-3/+7	±7	±14	±7	±14	N/A
Days Since Vaccination	-	0	7	14	21	28	84	178	268	358	
ICF, demographics, concomitant medications, medical history ²	X										
Confirm participant meets inclusion and exclusion criteria	X	X									
Physical examination ³	X	X	X			X	X	X		X	X
Vital signs ⁴	X	X									X
Pregnancy testing ⁵	X	X									
Randomization		X									
Dosing											

Visit Number		1	2			3	4	5		6	USV
Type of Visit	C	C	C/SC	SC	SC	C	C	C	SC	C	C
Month Timepoint		M0				M1	M3	M6	M9	M12	Up to M12
Study Visit Day	Screening ¹	D1 (Baseline)	D8	D15	D22	D29	D85	D179	D269	D359/EoS	USV
Window Allowance (Days)	-28		+3	+3	+3	-3/+7	±7	±14	±7	±14	N/A
Days Since Vaccination	-	0	7	14	21	28	84	178	268	358	
Study injection (including 15-minute post-dosing observation period)		X									

Visit Number		1	2			3	4	5		6	USV
Type of Visit	C	C	C/SC	SC	SC	C	C	C	SC	C	C
Month Timepoint		M0				M1	M3	M6	M9	M12	Up to M12
Study Visit Day	Screening ¹	D1 (Baseline)	D8	D15	D22	D29	D85	D179	D269	D359/EoS	USV
Window Allowance (Days)	-28		+3	+3	+3	-3/+7	±7	±14	±7	±14	N/A
Days Since Vaccination	-	0	7	14	21	28	84	178	268	358	
Surveillance for COVID-19											
Surveillance for COVID-19/Unscheduled visit ⁶	X	X	X	X	X	X	X	X	X	X	X
Nasopharyngeal swab ⁶		X				X	X	X		X	X
Blood for SARS-CoV-2 surveillance		X				X	X	X		X	
eDiary activation for surveillance for COVID-19/Unscheduled visit						X					
eDiary prompts every 2 weeks for surveillance for COVID-19 and major changes in health						eDiary prompts every 2 weeks (Day 43 through Day 359/EoS)					

Visit Number		1	2			3	4	5		6	USV
Type of Visit	C	C	C/SC	SC	SC	C	C	C	SC	C	C
Month Timepoint		M0				M1	M3	M6	M9	M12	Up to M12
Study Visit Day	Screening ¹	D1 (Baseline)	D8	D15	D22	D29	D85	D179	D269	D359/EoS	USV
Window Allowance (Days)	-28		+3	+3	+3	-3/+7	±7	±14	±7	±14	N/A
Days Since Vaccination	-	0	7	14	21	28	84	178	268	358	
Immunogenicity Assessment											
Blood for humoral immunogenicity ⁷		X				X	X	X		X	
Blood for cellular immunogenicity in a subset of participants ⁷		X	X								
Safety Assessments											
eDiary activation for recording solicited adverse reactions (7 days) ⁸		X									
Review of eDiary			X								
Follow-up safety			X	X	X				X		
Recording of Unsolicited AEs		X	X	X	X	X					

Visit Number		1	2			3	4	5		6	USV
Type of Visit	C	C	C/SC	SC	SC	C	C	C	SC	C	C
Month Timepoint		M0				M1	M3	M6	M9	M12	Up to M12
Study Visit Day	Screening ¹	D1 (Baseline)	D8	D15	D22	D29	D85	D179	D269	D359/EoS	USV

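### Symptomatic COVID-19 incidence rates count cases only from 14 days after randomization but divide by person-time from randomization, so rates and Poisson limits are too low

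*SAP*

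**What the plan says.** SAP 6.5.1.3 describes "symptomatic SARS-CoV-2 infection starting 14 days after randomization is an exploratory endpoint in Part 1 and a secondary endpoint in Part 2". Its counting rule is "Cases will be counted starting 14 days post randomization", and it applies to both the protocol and the CDC case definitions.

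SAP 6.5.2 takes the incidence rate as cases divided by total person-time and gives a 95% exact Poisson interval adjusted by that person-time. The clock starts at randomization: "Person-time is defined as the total time from randomization date to the date of event". It stops at the earliest of several dates, the last two being the "date of additional booster outside of the study or efficacy data cutoff date, whichever is earlier". The same section says: "Participants who received this additional booster may be censored in the efficacy analyses at the time of booster, as outlined below".

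Overall infection (SAP 6.5.1.1) is also counted from 14 days, but it is dated by the test. One possible date is the "Date of positive serology test result based on bAb specific to SARS-CoV-2 nucleocapsid". For overall infection only, the SAP adds: "Supportive analyses will summarize incidence of SARS-CoV-2 infection in which a case is counted after randomization".

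**The concern.** A rate describes a period at risk only when its numerator and denominator cover the same period. Here the first 14 days add person-time but cannot add a symptomatic case. Nothing in the SAP offsets the clock. The mITT and PPSE sets exclude on baseline infection status, not on a case documented before the 14-day point. Nor does the SAP say whether such an early case ends person-time, leaves the participant at risk, or removes the participant from the risk set.

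Symptomatic COVID-19 is a secondary endpoint in Part 2, and the per-arm rate with its exact interval is a planned output in its own right. Protocol 9.6.2 commits to incidence rates and says only that vaccine efficacy may be estimated if cases suffice.

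Two related points need care:

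- **Infection endpoints.** In SAP Appendix E, the routine swab and the row "Blood for SARS-CoV-2 surveillance" have no entry between Day 1 and the Day 29 visit. An infection acquired in the first 14 days but first found at Day 29 is dated then and still counts. The direction of any error is therefore uncertain, and a 14-day clock could overstate those rates.
- **Outside booster.** Censoring is worded as optional, while person-time always stops at the booster. If a participant is not censored, a later case could count with no matching person-time.

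**Working it through.** The documents state no case count, attack rate or efficacy power, so there is no figure of the plan's own to reproduce.

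**Inputs.** Days since vaccination at Month 3, Month 6 and Month 12 are 84, 178 and 358 (Schedule of Events). The lag is 14 days (SAP 6.5.1.3). Assumed, because the documents give none: a constant hazard h of 0.0005, 0.001 or 0.002 per day, and 100 or 200 expected cases in an arm.

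**Step 1: low-incidence limit.** Written rate / matched rate = (T − 14)/T.

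| T (days) | Ratio | Understatement |
|---|---|---|
| 84 | 70/84 = 0.833 | 16.7% |
| 178 | 164/178 = 0.921 | 7.9% |
| 358 | 344/358 = 0.961 | 3.9% |

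**Step 2: mixed follow-up.** Suppose half of participants stop at 84 days for an outside booster and half reach 358 (assumed). Mean follow-up is 0.5 × 84 + 0.5 × 358 = 221 days, and 14/221 = 6.3%. Uptake from 0% to 100% spans 3.9% to 16.7%.

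**Step 3: first events, constant hazard.** With S(t) = exp(−ht), cases per participant are S(14) − S(T). If an early case ends person-time, the written person-time is [1 − S(T)]/h and the matched person-time is [S(14) − S(T)]/h. The table shows written rate / true rate for the three hazards, under each reading of an early case.

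| T | Ends person-time | Leaves entirely | Stays in |
|---|---|---|---|
| 84 | 0.830 / 0.827 / 0.821 | 0.831 / 0.828 / 0.824 | 0.825 / 0.817 / 0.799 |
| 178 | 0.918 / 0.915 / 0.908 | 0.918 / 0.915 / 0.909 | 0.912 / 0.902 / 0.880 |
| 358 | 0.957 / 0.954 / 0.946 | 0.958 / 0.954 / 0.947 | 0.950 / 0.939 / 0.911 |

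A clock starting at 14 days among those still event-free gives 1.000 throughout.

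**Step 4: interval coverage.** This is the probability that the nominal 95% exact Poisson interval, scaled by (T − 14)/T, contains the rate for the period in which cases can count.

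| | 100 expected cases | 200 expected cases |
|---|---|---|
| Matched windows | 95.5% | 95.2% |
| T = 358 | 93.6% | 92.3% |
| T = 178 | 87.4% | 79.0% |
| T = 84 | 55.3% | 24.9% |

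**Step 5: vaccine efficacy.** Take a true 30%, so the hazard in the investigational arm is 0.7h. One minus the ratio of written rates, over all T and h, is 29.7% to 29.9% if an early case ends person-time or leaves, and 28.7% to 29.8% if it stays in.

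**Step 6: infection endpoints.** Let f be the share of infections acquired in the first 14 days that are first found at a scheduled visit. The documents do not give f, so it runs from 0 to 1. As written, the ratio to the true rate is (T − 14 + 14f)/T. With a 14-day clock it is (T − 14 + 14f)/(T − 14).

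| T | As written, f = 0 / 0.5 / 1 | 14-day clock, f = 0 / 0.5 / 1 |
|---|---|---|
| 84 | 0.833 / 0.917 / 1.000 | 1.00 / 1.10 / 1.20 |
| 358 | 0.961 / 0.980 / 1.000 | 1.00 / 1.02 / 1.04 |

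**The case against.** The strongest reply is that little hangs on this. Both arms of a 1:1 active-controlled trial carry the same 14 days, so the comparison is nearly unchanged. Efficacy has no hypothesis, alpha or power statement, and no absolute rate is set against a benchmark. That is correct and limits the weight of the point. It does not make the per-arm rates right.

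The 84-day figures are an extreme. They need everyone to stop at Month 3, whereas unblinding is optional and comes only after Month 6 in Part 1. In addition, 200 cases at 84 days among 1328 participants would need a hazard of about 0.0024 per day, slightly above the assumed range, and the PPSE is smaller than 1328. So the 24.9% coverage marks the far end and is not an expectation. Coverage is also judged against the rate after 14 days. That is the endpoint SAP 6.5.1.3 defines, although it is not the ratio that 6.5.2 literally writes down.

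SAP 6.5.3 allows sensitivity analyses with case counting started at other times, and a count from randomization would match the clock. That analysis is optional, moves only the numerator, and leaves the main rate as it is.

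The booster wording can be read together with the person-time rule that follows it, which makes the intent fairly clear. It is a minor drafting point. Finally, the remedy puts symptomatic and infection rates on different clocks. That is a real cost in presentation, but it follows from how each event is dated.

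**Conclusion.** The concern holds. As written, the symptomatic COVID-19 rate and both exact Poisson limits are too low for the endpoint the SAP defines. The low-incidence shortfall is 3.9% with full follow-up to Month 12, 7.9% to Month 6 and 16.7% to Month 3. It is 6.3% if half of participants take an outside booster right after Month 3, which is an assumption. Under the assumed hazards the shortfall is somewhat larger, most of all if participants with early cases are kept at risk.

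The effect on vaccine efficacy is at most 1.3 percentage points from a true 30%. Counts, percentages and the primary immunogenicity tests are unaffected. For overall and asymptomatic infection the direction cannot be settled from the documents, and the written rate lies between 0.83 and 1.00 of the true rate at 84 days. This should be corrected, but it does not threaten the trial's main conclusions.

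**What to change.** In SAP 6.5.1 and 6.5.2:

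1. For the main symptomatic COVID-19 rates, under both case definitions, start person-time 14 days after randomization among participants event-free and in follow-up at that point. State that a participant with a documented case before then leaves the risk set.
2. Do not apply that clock to overall or asymptomatic infection. Report the count from randomization over person-time from randomization as the matched rate. SAP 6.5.1.1 already plans that count for overall infection; add it for asymptomatic infection. Alternatively, state that test-dated infections may have been acquired before the 14-day point.
3. Replace 'may' with 'will' for censoring at the outside COVID-19 booster, so that case counting and person-time end on the same date.
4. Label each rate in the tables with its clock.

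The cost is a few sentences and a small programming change. Protocol 9.6.2 leaves efficacy details to the SAP, but at this stage the change should be recorded as a dated SAP revision. Reported COVID-19 rates become slightly higher. The risk set loses 1 − exp(−14h) of participants before the 14-day point: 0.7%, 1.4% or 2.8% at the three assumed hazards.
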